**[name]**

**Advisor: [name] [name]**

**NCT Number: NCT05503680**

**Document date: January 7th, 20223**

## 1. Yoga protocol intervention

[figure not shown]
Participants in the yoga group engaged in eight biweekly online Hatha yoga classes for 120 minutes each at home. Classes began with 15 minutes of sitting meditation; breathing exercises; shoulder, neck, and back stretches; and sun salutations (either seated or standing). Following that, ten minutes of standing poses, fifteen minutes of balancing poses, and ten minutes of abdominal and back-bend positions will be performed. After 10 minutes of cool-down stretches and a final time of rest, all sessions was concluded. Physical postures and supportive props were modified to accommodate participants of all abilities. Participants was given an honorarium of Rp 50.000 or 3.49 USD at the baseline and final assessments. The full version of the yoga protocol is available in appendix III.

Table 3: Yoga protocol

Position	Main content	Length time
1. Warm-up	(1) Seated meditation, (2) Alternate (3) Nostril breathing, (4) Bellows breath, (5) Shoulder/neck stretches, (6) Cat-cow forward fold, (7) Sun salutations.	10 minutes
2. Standing poses	(1) Warrior one, (2) Warrior two, (3) Triangle, (4) Extended side angle, (5) Reverse warrior, (6) High lunge with twist.	10 minutes
3. Balance poses	(1) Tree pose, (2) Standing holding knee, (3) Modified warrior three (chair support), (4) Half-moon.	10 minutes

4. Abdominal and back bends	(1) Bird-dog, (2) Side plank, (3) Bridge, (4) Cobra, (5) Sphinx, (6) Baby position	10 minutes
5. Meditation	Full lotus, half lotus, Burmese	10 minutes
6. Cool down	(1) Twist, (2) Cobbler's pose, (2) Hip (3) Stretches, (4) Corpse pose, (5) Side-lying, (6) Seated on.	10 minutes

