**All rights reserved**

## **Preface**

This 60-minute yoga protocol was developed for participants in the research project, "The effect of a yoga intervention for reducing stress among people living with HIV during the covid-19 pandemic in Indonesia, a randomized controlled trial."

You have been given a copy of this protocol because you are an HIV positive person and are undertaking a yoga intervention program to reduce stress. This protocol has an instructor and pictures of yoga poses to help you to practice yoga correctly. Share this protocol with your family, friends, or community who might need help to recover from stress related to HIV.

[name]

Doctoral student

February 3rd, 202

Position	Activity/purpose	Action plan		
Warm up (15 minutes)	
Activity:            (1) Seated meditation, (2) Alternate nostril breathing, (3) Bellows breath, (4) Shoulder/neck stretching, (5) Cat-cow forward fold, (6) Sun-salutation.
 
Maximum duration: 15 minutes
 
Purpose:
 
 
• Warming up for hatha yoga aims to help participants to prepare their minds to be centered, calm, and focused.
 
• A distracted mind prevents participants from reaping the deepest psychological and spiritual benefits from yoga practice.
 
 
Equipment:            Yoga mattress, chair, sport clothes, chair
	 1. Seated meditation	 2. Alternate nostril breathing	 3. Bellows breath

		
coming in and going out, letting thoughts float away like logs rolling down the river.
	
through the right side. Next inhale through your right nostril, then close it as you open the left nostril and exhale through the left side. This is one cycle. Repeat 5 times.
	
inhalation happening in between. Make sure the breath comes from your diaphragm, with your belly moving in and out. head, neck, shoulders, and chest

		 
4. Shoulder/neck stretching
	 
5. Cat-cow forward fold
	 
6. Sun salutation

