		
Instruction: sit as in seated meditation. Place one of your hands behind your back with the other hand on top of your head. With the hand on your head, gently pull your ear toward your shoulder. Feel the stretch at the side of the neck. Hold it for 20 seconds and repeat three times. Then
	
Instruction: Begin on your hands and knees in the table pose, with your spine relaxed. As you exhale, come into cat pose by rounding your spine outward like a cat arching its back, tucking your tailbone in, and drawing your stomach in. Next, as you inhale, move into cow pose by lifting your sit bones
	
Instruction: Begin in a standing position with your feet slightly apart and parallel to each other, your palms turned out, and shoulders relaxed. Then follow this sequence of positions: mountain pose (i.e., standing with the palms of your hands facing towards your body alongside your thighs), Inhaling, lift both

repeat these steps for the other side.

upward, pressing your chest down and forward, lifting your head up and allowing your belly to sink. Relax your shoulders away from your ears, gazing straight ahead.

arms up. Exhaling, fold forward at the hips bringing your hands down to the mat. Step the right leg back and lunge. Then step the left leg back in plank, keeping body parallel to the floor. Then, bending your elbows bring the chest down to the ground. Push up with your hands, straightening the elbows and sliding forward into up dog. Curl the toes under, press down on feet and hands, lifting your hips up. Straighten elbows and knees. Then step your right foot forward so your right foot is parallel with your hands. Bring left foot up to the right foot and you are standing flexed at the hips in forward fold. Inhaling and standing up, swoop the arms out to the sides and above your head. Bring the palms together

				and lower them to your heart in namaste and back to mountain pose. The yoga instructor will demonstrate how to do this.

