### **3. Statistical analysis plan**

Before performing statistical procedures, all data was entered into a computer and checked for errors. To analyze the data, the researcher then used SPSS computer software version 20. The data for all variables was manually coded before using the SPSS application, including demographic characteristics of patients, the perceived stress scale results brief health status survey, and coping self-efficacy. The alpha value was set at  $\alpha=0.05$  to determine the statistical significance of the variables. For demographic characteristics, the data analysis was descriptive statistics to identify the frequencies and percentages for categorical variables and the means and standard deviations for continuous variables. Before the statistical data processing begins, the data for independent and dependent variables was tested to determine its distribution and normality using plot histograms, logs and square roots, and checking residuals.

This study took repeated assessments over time and used a Generalized Estimating Equation (GEE) approach to model each study outcome and to predict the relationship of the variables while accounting for correlated data within the repeated measures (Hardin & Hilbe, 2007). The GEE technique, introduced by Liang and Zeger (1986), was the most often used strategy in marginal models, and it was a variation of Generalized Linear Modelling (GLM). GEE can handle correlated data with discrete, continuous, or binary outcomes. GEE is a non-likelihood or quasi-likelihood data modeling approach that specifies one of many working correlation matrix architectures to account for within-subject correlations (Liang & Zeger, 1986).

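### The GEE is described as handling correlation within a participant's repeated measures and names no class level; if yoga participants shared classes, the standard error of the yoga effect could be somewhat too small

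*Combined protocol and SAP*

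**What the plan says.** Section 3 of the SAP states that the study "used a Generalized Estimating Equation (GEE) approach to model each study outcome" while "accounting for correlated data within the repeated measures". It adds, as a general account of the method, that GEE "specifies one of many working correlation matrix architectures to account for within-subject correlations". It names no class, instructor or other grouping of participants, and it sets alpha at 0.05.

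On delivery, section 1 says: "Participants in the yoga group engaged in eight biweekly online Hatha yoga classes for 120 minutes each at home". In the pose table after the Preface, the sun salutation entry ends: "The yoga instructor will demonstrate how to do this". The Preface calls the study "a randomized controlled trial".

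The available text does not give the number or size of classes, the number of instructors, whether participants attended the same live sessions, the sample size, the allocation ratio or how the control arm was handled.

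**The concern.** Randomising individuals makes participants independent at allocation. It does not keep them independent if members of one arm are then taught together. Classmates share an instructor, a pace and a group, and their outcomes can become alike. In a GEE clustered on participant, the robust variance protects against a wrong correlation structure within a person. It does not protect against correlation between people, and a different working correlation matrix does not change that.

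If such correlation exists in the yoga arm, the confidence interval for the yoga-control difference is too narrow and the 5% test rejects too often. A borderline result could depend on it. Without the class counts, a reader cannot tell whether the reported precision is right.

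**Working it through.** **Inputs from the documents.** Alpha 0.05 (SAP section 3; two-sided is assumed, since sidedness is not given) and a GEE described at the within-participant level. The plan states no sample size, standard deviation or ICC, so it has no figure of its own to reproduce.

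**Assumed inputs.** 1:1 arms, equal total variance in both arms, ungrouped controls, yoga classes of equal size m, and an ICC of 0 to 0.05.

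**Which correlation matters.** With two time points and complete data, the group-by-time term of a participant-clustered exchangeable GEE equals the difference in mean change, with its participant-level robust SE. This was confirmed on generated data. The ICC below therefore refers to change from baseline. A class effect equal at every visit cancels: simulated with 40 per arm, m = 10 and ICC 0.10, the true SE was 0.217 against a model SE of 0.215, with 5.5% rejections.

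**Formulas.**
- Design effect in the yoga arm: DE = 1 + (m - 1) x ICC.
- True SE / model SE: F = sqrt((DE + 1)/2).
- Type I error = 2 x (1 - Phi(1.96/F)).

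Example, m = 10 and ICC 0.05: DE = 1 + 9 x 0.05 = 1.45; F = sqrt(2.45/2) = 1.107; 1.96/1.107 = 1.771; type I error = 7.7%.

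| Class size | ICC 0 | 0.01 | 0.02 | 0.05 | F at 0.05 |
|---|---|---|---|---|---|
| 5 | 5.0% | 5.2% | 5.5% | 6.2% | 1.049 |
| 10 | 5.0% | 5.5% | 6.0% | 7.7% | 1.107 |
| 20 | 5.0% | 6.1% | 7.2% | 10.7% | 1.214 |

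**Finite-sample check.** Simulated with 60 per arm (assumed) and 100,000 runs per cell, the participant-clustered test rejected as follows at ICC 0 and 0.05: twelve classes of 5, 5.5% and 6.8%; six of 10, 5.5% and 8.2%; four of 15, 5.5% and 9.9%. The 0.5 points above 5% at ICC 0 are small-sample error of the robust SE and have nothing to do with classes.

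**Which sensitivity analysis holds its level.** Class means with Satterthwaite degrees of freedom, over ICC 0 to 0.05, rejected 5.0-5.2% with twelve classes, 5.1-5.2% with six, 5.4-5.8% with four, 5.8-6.6% with three and 7.0-9.4% with two. This is the reason for a cut at four classes. With four classes, the alternatives behave differently: a class-clustered GEE with a Kauermann-Carroll correction and normal reference rejected 7.0-8.0%, the same with a Mancl-DeRouen correction 5.5-6.3%, and a partially nested REML model with Satterthwaite degrees of freedom 3.5-4.6%.

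**Cost in interval width.** With n = 60 per arm and k classes, df = (DE + 1)^2 / (DE^2/(k - 1) + 1/(n - 1)). For k = 4 and ICC 0.05: m = 15, DE = 1 + 14 x 0.05 = 1.70, df = 7.29/(0.963 + 0.017) = 7.4, and the t quantile is 2.337. The unclustered quantile on 118 df is 1.980. The width ratio is 1.162 x 2.337/1.980 = 1.37. By the same route, the ratio at ICC 0 is 1.02, 1.06 and 1.11 for twelve, six and four classes; at ICC 0.05 it is 1.08, 1.20 and 1.37.

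**The case against.** The strongest reply is that the triggering fact is missing. No passage says that participants attended together. Classes were online and taken at home, and the line about the instructor comes from a handout addressed to a single reader. Individual or recorded delivery is not excluded. This stands, and it is why the point is conditional.

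A reader might infer three stronger things that the documents do not support:
- **That the plan allows for correlation within participants and nowhere else.** Section 3 does not say so. Its sentence on working correlation matrices is a general description of GEE, not a specification of this trial's clustering variable. What can be said is that no class level is named.
- **That the trial's type I error is above 5%.** Class size, ICC, arm sizes and the handling of controls are all assumed. At classes of 5 to 10 and ICC 0.01 to 0.02 the error is only 5.2-6.0%.
- **That any class-clustered model would do better.** With four classes, the Kauermann-Carroll version rejected 7.0% at ICC 0, against 5.5% for the planned GEE.

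It can also be said that the public text looks like an extract, since section 1 numbers its table as Table 3 and refers to an appendix III. A fuller document may describe the classes. That is possible, and one sentence from it would then settle the question.

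**Conclusion.** The point holds in conditional form. The SAP names no class or instructor level, and shared classes are the natural reading of the delivery, but they are not stated. If classes were shared and a positive class correlation in change arises after baseline, the SE of the yoga-control difference is too small. Under the assumptions listed, the factor reaches 1.05, 1.11 and 1.21 at ICC 0.05 for classes of 5, 10 and 20. If sessions were individual, or the ICC is zero, nothing changes. The direction is certain given the two conditions; the size cannot be fixed from the documents. Severity is minor: a cheap improvement, not a fault in the main analysis.

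**What to change.** 1. Keep the planned GEE as the main analysis, with its confidence interval unchanged.
2. State whether yoga participants shared classes, and report the number and size of classes and the number of instructors. If a participant changed class, use the first class and say so. If sessions were individual and instructors many, one sentence closes the matter.
3. If classes were shared and there were four or more, add one named sensitivity analysis on change from baseline. Compare the yoga class means with the controls, each control as his or her own unit, using Satterthwaite degrees of freedom. If controls also met in groups, use group means in that arm too. Name this one method now, so that the model is not chosen after the results are seen.
4. Report both intervals. If only one excludes zero, qualify the conclusion; neither analysis should decide alone.
5. With one to three classes, or one instructor, state that the class or instructor effect cannot be reliably separated from the yoga effect. Show the main interval with the SE multiplied by sqrt((2 + (m - 1) x ICC)/2) for ICC 0.02 and 0.05, labelled as assumed values. Here m is the number of participants who shared a class or instructor, and the formula is for equal arms.

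The cost is a class identifier and an instructor identifier from the session records, one extra analysis and a wider sensitivity interval. Assuming 60 per arm, that interval is about 2-11% wider at ICC 0 and 8-37% wider at ICC 0.05, for twelve down to four classes. The SAP is written in the past tense, so the identifiers may no longer exist; if so, report the counts alone.
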